5.6.2 Analysis strategies

Baseline clinical and socio-demographic characteristics will be compared between groups to identify any chance differences that may have occurred despite random assignment. Outcome variables will be screened to determine whether they meet assumptions of normally distributed random variables with equal variances, and a descriptive examination will be performed, including plotting of relationships by condition. Retention rate will be computed by condition.

For the primary analyses, group differences in objectively measured and self-reported sedentary time (using the average of seven days) over the two time points (baseline and 8 weeks) will be examined using independent t-tests for parametric variables and Wilcoxon Mann Whitney test for nonparametric

variables. Similar analysis techniques will be used for secondary outcomes of interest (i.e., *activPAL*-measured and self-reported weekly MVPA; BMI, waist circumference, total cholesterol, HDL, LDL, triglycerides, fasting blood glucose, blood pressure, resting heart rate, aortic stiffness, HRQoL scores, self-efficacy scores, HADS scores, and maximum aerobic capacity).

Table 1. Study measurement timeline.

Visit	Screen	Baseline week	Cardiac rehabilitation							
			Week 1	Week 2	Week 3	Week 4	Week 5	Week 6	Week 7	Week 8/ follow-up
Length of time needed	30 min	1-2 hours	45 min	30 min	30 min	30 min	30 min	30 min	30 min	1-2 hours
Informed consent	C, I									
Diagnosis	C, I									
Age	C, I									
Sex (male/female)	C, I									
Height		C, I								
Weight		C, I								C, I
Waist circumference		C, I								C, I
Blood pressure (Mobil-O-Graph)		C, I								C, I
Resting heart rate (Mobil-O-Graph)		C, I								C, I
Blood work (cholesterol, HDL, LDL, triglycerides, HbA1c)		C, I								C, I
MVPA (CR questionnaire + activPAL3)		C, I								C, I
Questionnaires (self-efficacy, HRQoL, anxiety/depression)		C, I								C, I
Aortic stiffness (Mobil-O-Graph)		C, I								C, I
Aerobic power (Bruce Treadmill Test)			C, I							C, I
Sedentary time (activPAL3™, IPAQ, CR Questionnaire)		C, I								C, I
7-day activity journal (FITS)		C, I								C, I
Wear-time log			I	I	I	I	I	I	I	
Sedentary feedback (VTAP)			I	I	I	I	I	I	I	
Feedback survey										C, I

C - Control group, HDL - high-density lipoprotein, HRQoL - health-related quality of life, I - Intervention group, IPAQ - International Physical Activity Questionnaire, LDL - low density lipoprotein, MVPA - moderate-to-vigorous intensity physical activity

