5.0 METHODS

5.1 Study design

This is a single-centre, two-armed randomized controlled trial (RCT) to evaluate the feasibility and usability of the *activPAL3™* in measuring sedentary time and the VTAP in providing sedentary prompts to reduce sedentary time in a CR setting (SIT-CR Study). The RCT (see **Figure 1** for study flow) will randomly allocate 32 individuals (16 males and 16 females) in a 1:1 ratio entering the CR program to either the Control Group (CR program) or to the Intervention Group (CR program + sedentary prompts from VTAP).

A week prior to their first class, participants will be asked to come to the UOHI to complete informed consent, a short questionnaire to assess employment patterns, self-efficacy to reduce sedentary behaviour and increase light and moderate PA, and HRQoL (see SIT-CR Study Baseline and Follow-up Questionnaires). Participants will also have their aortic stiffness, blood pressure and resting heart rate measured. In order to test for aortic stiffness participants will be asked to fast if possible, the study will provide a package of nuts and a glass of water at this first meeting. After the measurements, participants will then be asked to wear an *activPAL3™* during waking time for 7 days to collect baseline measures of sedentary time over one week prior to their first CR class.

On the day of their first CR class, participants will be asked to come in 30 minutes early to complete a Modified Bruce Ramp Treadmill Test to estimate maximal aerobic power. Once the test is complete, participants will be randomized in a 1:1 ratio (stratified by sex) to the Intervention or Control Groups. At this visit, participants in the Intervention Group will receive a wear time log sheet and a VTAP

monitor that will provide sedentary prompts to break up prolonged periods of sedentary time (prompts after 30 minutes of sedentary time). Participants in the Intervention Group receive a full-charged VTAP monitor each week when they attend their on-site CR class. Participants in the Control Group will continue with their regular CR class schedule.

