5.5 Measures

The primary objective of this study is to assess the feasibility and usability of the *activPAL3™* and the VTAP in a CR setting to inform the development of a larger RCT. This will be assessed by examining:

- Recruitment rates;
- acceptability of intervention and wearing the *activPAL3™* and the VTAP using an evaluation survey (see Evaluation Surveys);
- completion and drop-out rates; and
- intervention adherence using wear time logs.

The primary outcome of the intervention focuses on changes in sedentary time measured by self-report and the *activPAL3™* over the 8-week intervention period. These outcomes will provide standard deviations to estimate an effect size for a future RCT. Secondary outcome measures will include:

- changes in MVPA (self-reported and objectively measured);
- changes in clinical outcomes (e.g., body weight, BMI, waist circumference, blood pressure, total cholesterol, HDL, LDL, triglycerides, and fasting plasma glucose);
- changes in measures of anxiety and depression (HADS);
- changes in self-efficacy to reduce sedentary time and increase PA;

- changes in HRQoL (SF-36);
- changes in aortic stiffness (PWV); and
- changes in maximal aerobic power (Modified Bruce Ramp Treadmill Test).

Measures and study time-line are provided in **Table 1**.

5.5.1 *Sedentary time*

The primary objective of this study is to evaluate the feasibility and usability of the *activPAL3™* in collecting time spent sitting, standing and lying in an on-site CR program. From this, the primary outcome of the RCT will be changes in sedentary time as measured both by self-report (sitting time from the International Physical Activity Questionnaire [see SIT-CR Baseline and Follow-up Questionnaires], sitting time from a FITS log [see SIT-CR Baseline and Follow-up Questionnaires], a sitting time question from the CR intake questionnaire), and objectively measured by the *activPAL3™* over 7-days. See the provided PAL Technologies Ltd. End User Licence Agreement.

5.5.2 *Moderate-to-vigorous intensity physical activity (MVPA)*

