5.5.13 Covariates

The following are possible confounders that will be used in the analysis.

Age: Each participant's age will be extracted from the CR patient file.

Sex: Participant's sex will be extracted from the CR patient file.

Education: Participant education is self-reported as part of the CR intake questionnaire and is defined as the highest education level attained from Grade 6 or less, up to 4+ years of college/university.

Marital status: Participant marital status is self-reported as part of the CR intake questionnaire, it is categorized as: "single", "married/common law", "divorced/separated", or "widowed".

Occupational status: Participants' current occupational status is self-reported as part of the CR intake questionnaire and is categorized as: "Full time, working for pay (35 hrs or more/wk)", "retired", "part time, working for pay", "unemployed (looking for work)", "not working, but have a job to return to (e.g. sick leave)", "unemployed", "not/never employed outside the home", or "presently on disability leave".

Occupation activity: Participants that are currently working, will be asked to rate their current occupation activity using the following categories: "mostly sedentary (e.g., desk-based job)",

"moderately active (e.g., mix of desk-based job and walking about)", "active and on your feet most of the time (e.g., teacher, nurse)", or "very active and physical (e.g., mail carrier, manual labour)"

Number of people in the household: Participants will be asked for the number of people in their household.

Season: The season/time of year the participant completed the majority of the intervention will be collected.

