5.6 Statistical considerations

5.6.1 Sample size calculation

Pilot/feasibility studies are generally not designed with the power to detect intervention effects, which is the intention of future definitive trials. Pilot/feasibility studies are often carried out to be able to estimate an effect size for a larger trial. However, to provide guidance, we have estimated a sample size based on previous study effect sizes to detect differences in sedentary time. G*Power Version 3.1.9.2 power analysis and sample size software was used to calculate the sample size [23]. A minimal clinically important difference (MCID) for reductions in sedentary time (i.e. substituting sedentary time for light or moderate+ intensity PA) associated with improvements in cardiometabolic health, health-related quality of life and reduced mortality, has been estimated to be 30-60 minutes/day [24-26], with a cumulative effect (i.e. more is better). Unfortunately, as this study is a pilot-level RCT, there are not adequate resources to accommodate a large enough sample size to detect differences in 30 minute/day. Rather, there will be adequate power to detect a difference of 91 minutes/day, which was the average reduction in sedentary time from sedentary interventions found by the authors in a recent systematic review [6]. A total sample size of 32 participants, 16 per arm, is needed to detect a 91 minute/day difference in sedentary time at a 0.05 significance level with 80% power, an addition of 10% for those who do not complete the trial, and 5% for data missing at random, assuming a standard deviation of 94 minutes/day as found in a recent evaluation of sedentary time among CR graduates from the UOHI [5]. This sample size is sufficient to test the research hypothesis using t-tests to measure the difference in sedentary time between the intervention and control groups.

When the study is close to completion a sample size recalculation will be undertaken by the Research Methods Centre at the UOHI.

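### Section 5.6.2 leaves open whether change or the week-8 value is tested and adjusts for neither baseline, sex nor the listed covariates; prespecify ANCOVA on baseline and sex

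*Combined protocol and SAP*

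**What the plan says.** - **Test.** Section 5.6.2 compares sedentary time between the groups "over the two time points (baseline and 8 weeks) will be examined using independent t-tests for parametric variables and Wilcoxon Mann Whitney test", and plans similar techniques for the secondary outcomes. A two-sample test needs one number per participant, and the section does not name it.
- **Choice of test.** It follows inspection of the outcome data: "Outcome variables will be screened to determine whether they meet assumptions of normally distributed random variables with equal variances".
- **Outcome.** Section 5.5: "The primary outcome of the intervention focuses on changes in sedentary time measured by self-report" and by activPAL3. Section 5.5.1 also defines the outcome as change.
- **Sample size.** Section 5.6.1 calls 32 participants "sufficient to test the research hypothesis using t-tests to measure the difference in sedentary time" between the groups, "assuming a standard deviation of 94 minutes/day as found in a recent evaluation of sedentary time among CR graduates from the UOHI". That SD is not described as an SD of change.
- **Stratification.** Section 5.1: "participants will be randomized in a 1:1 ratio (stratified by sex) to the Intervention or Control Groups". Section 5.4.2 repeats this. No planned analysis uses the stratum.
- **Covariates.** Section 5.5.13: "The following are possible confounders that will be used in the analysis". Eight variables follow, including age, sex, occupational status and season. Section 5.6.2 names no analysis that could use them.

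**The concern.** The sections do not fit together. The outcome definition points to a change score, the sample size assumption reads like a single-time comparison, and section 5.6.2 does not settle which is tested. The covariate section promises an adjustment that the named tests cannot make.

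Three things are at stake. First, the change test and the week-8 test can differ widely in power on the same data, in either direction depending on r. Second, eight candidate covariates, one of them with eight categories, cannot all be fitted to about 28 participants, so any adjusted result would rest on a selection made after the data are seen. The switch between t-test and Wilcoxon is open in the same way. Third, section 5.5 wants these outcomes to supply SDs and an effect size for a larger trial. The single-time SD, the change SD and the residual SD are different quantities, so the one to carry forward depends on the model.

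**Working it through.** **Inputs.** From section 5.6.1: difference 91 min/day, SD 94, significance level 0.05, power 80%, N = 32, with 10% and 5% added for losses. Sidedness is not stated. The correlation r between baseline and week 8 is not given and is assumed over a range.

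**Reproducing N = 32.** The standardised difference is 91/94 = 0.968. With 14 per arm the noncentrality is 0.968 × √(14/2) = 2.56 on 26 df. Power is 80.2% one-sided and 69.4% two-sided. Inflating 28 gives 28 × 1.15 = 32.2. So 32 corresponds to a one-sided t-test with 14 evaluable per arm. Two-sided, 80% power would need 18 per arm before losses.

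**Formulas**, with s the SD of one measurement, equal at both times:
- week-8 t-test: SD = s, 26 df
- change t-test: SD = s√(2(1−r)), 26 df
- ANCOVA (arm, baseline, sex): residual SD = s√(1−r²), 24 df

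The t-test powers are exact (noncentral t). The ANCOVA powers come from 40,000 simulated trials per setting, bivariate normal, with 7 of each sex per arm.

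**(A) 94 is the SD of one measurement.** Two-sided power, 14 per arm:

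| r | Change SD | Week-8 t | Change t | ANCOVA |
|---|---|---|---|---|
| 0 | 132.9 | 69% | 41% | 67-68% |
| 0.2 | 118.9 | 69% | 50% | 69% |
| 0.3 | 111.2 | 69% | 55% | 71-72% |
| 0.5 | 94.0 | 69% | 69% | 79-80% |
| 0.7 | 72.8 | 69% | 89% | 92% |
| 0.9 | 42.0 | 69% | 100% | 100% |

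**(B) 94 is the SD of change.** Then s = 94/√(2(1−r)):

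| r | s | Week-8 t | Change t | ANCOVA |
|---|---|---|---|---|
| 0.2 | 74 | 88% | 69% | 87-88% |
| 0.5 | 94 | 69% | 69% | 79-80% |
| 0.7 | 121 | 48% | 69% | 74% |
| 0.9 | 210 | 20% | 69% | 69% |

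**Precision under (A), mean 95% CI half-width in min/day.** At r=0.5 it is 72 for either t-test and 64 for ANCOVA. At r=0.7 it is 72 (week-8), 56 (change) and 53 (ANCOVA).

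**Sidedness.** One-sided at r=0.5, the powers are 80, 80 and 88%.

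**Type I error at r=0.5.** About 5% for all three methods.

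**Sex.** The documents do not say how prognostic it is. If it explains 0, 10 or 20% of the variance of one measurement (r=0.5), ANCOVA power is about 80, 81 and 83%. Most of the gain comes from baseline.

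**The case against.** **Sections 5.5 and 5.5.1 both define the outcome as change, so a change-score t-test is the natural reading.** This largely stands. It is the likelier reading, and one added phrase would name the tested quantity. It would not bring in the stratum, give the section 5.5.13 covariates a place, or protect against a low r.

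**The benefit depends on an unknown r.** True. Against the change test, ANCOVA gains about 3 points under (A) and 5 under (B) at r=0.7, and nothing at r=0.9. The large gains occur at r of about 0.5 or below. But an unknown r is itself a reason for ANCOVA, which does not require guessing it.

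**The 69% starting point reflects unstated sidedness, so ANCOVA should not be credited with restoring 80%.** This stands as a caution. The shortfall from 80% is a separate matter. The comparison between methods holds either way, as the one-sided figures show.

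**This is a pilot whose primary objective is feasibility.** That limits the weight of the point. Even so, section 5.6.2 calls these the primary analyses, section 4.3 states superiority hypotheses and section 5.6.1 claims 80% power.

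**The simulations assume normal data with equal variances, and the response format of the cardiac rehabilitation questionnaire's sitting item is not given.** Both are correct. Skewed data were not examined, which is a reason to keep the Wilcoxon test as a sensitivity analysis and to confirm that the item is numeric before modelling it.

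**Conclusion.** The concern holds. Section 5.6.2 does not identify the tested quantity, uses neither baseline as a covariate nor the sex stratum, and gives the section 5.5.13 covariates no role. Nothing here invalidates the trial: the unadjusted tests are valid under randomisation, and the loss is in precision and in freedom to choose after the data are seen.

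Under (A), the unstated choice between the two t-tests is worth about 28 points of power in favour of week-8 at r=0 (69 − 41) and about 20 in favour of change at r=0.7 (89 − 69). ANCOVA matches or exceeds the better t-test, to within about a point, at every r examined except r near 0, where it loses up to about 2 points. These sizes rest on assumed values of r, normal data, equal variances and 14 evaluable per arm. This is a change that should be made because it is cheap.

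**What to change.** - **Section 5.6.2.** Prespecify that week-8 sedentary time is compared between arms by ANCOVA with arm, the baseline value of the same measure, and sex. Fit it for activPAL3 and separately for each self-report measure, and report the adjusted difference with a 95% CI. Use the same model for continuous secondary outcomes that have a baseline. Keep the Wilcoxon test as a named sensitivity analysis, not a switch decided after screening.
- **Section 5.5.13.** Limit the model covariates to baseline and sex, and say that the other listed variables are used descriptively. If the team wants another in a sensitivity model, name it now.
- **Section 5.6.1.** State that N = 32 was derived for an unadjusted t-test and that the analysis is ANCOVA.
- **Reporting.** Give the baseline, week-8, change and residual SDs and r for planning the next trial.

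**Cost.** Wording in three sections. No new data are needed, since Table 1 already schedules sedentary time at baseline and week 8 in both arms and records sex. The model spends two residual degrees of freedom, at most about 2 points of power against a week-8 t-test if r is 0.

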6.0 RESEARCH PLAN AND FEASIBILITY

6.1 Clinical relevance

Results from this study will provide important missing information regarding movement patterns and sedentary time in patients undergoing CR. Results of the trial will be useful for the design of a larger intervention trial to reduce sedentary time in CR patients and further improve patient-related clinical and behavioural outcomes. Additionally, results of this study will identify whether using the *activPAL3™* as a means of measuring sedentary time in a CR population is feasible, and whether the use of prompting devices are acceptable to patients.

6.2 Risks, benefits and usual standard of care

No changes will occur to the usual standard of care for patients enrolled in CR.

Participation in this study requires that participants wear an *activPAL3™* monitor taped (using stickers) to the front of the right thigh during waking hours for a minimum of 7 consecutive days (baseline and follow-up) and the VTAP monitor continuously during waking hours for weeks 1-7 in the intervention group. The PALstickies used to apply the *activPAL* devices are hypoallergenic and consist of a dual layer hydrogel that does not pull at skin or hair. They are used for waking day recordings and are removed when going to bed, showering or bathing and will therefore, be reapplied each morning. In order to reduce possible skin irritations, participants in the intervention group will be instructed to alternate the location and leg used over weeks 1-7. The monitors are not an intentional emitter or radiator of electric or magnetic fields and poses no risk to a person fitted with a pacemaker. Important to note however that there are some limitations to when the monitor can be worn during scans and testing. The table below outlines when it should be removed and will be provided in the information sheet to participants:

Scan/test	Affects activPAL	activPAL affects scan	Comment/action
MRI scan	YES	YES	Remove from test
CT scan	YES	YES	Remove from test
X-ray	NO	Yes if in imaged area	Remove if in imaged area
EMG	NO	MAYBE if in test area	Remove if thigh is tested
ECG	NO	NO	ECG electrodes are on chest
EEG	NO	NO	EEG electrodes are on chest

Participation in this study requires that participants perform an exercise test (Modified Bruce Treatment Test) and training sessions. The risk of cardiovascular events during exercise testing varies directly with the incidence of cardiovascular disease. The risk of exercise testing is low, with approximately 6 cardiac events per 10,000 tests (0.06%). This is comparable to the usual care that patients in cardiovascular rehabilitation programs would receive. Recent studies have reported a rate of 1 cardiac arrest per 116,906 patient-hours, 1 myocardial infarction per 219,970 patient-hours, 1 fatality per 752,365 patient-hours, and 1 major complication per 81,670 patient-hours in a cardiovascular rehabilitation setting. It should be noted that these rates are low and

likely due to the fact that patients in these studies were screened and exercised in a medically supervised setting equipped to handle emergencies. This is the case of the UOHI, Division of Prevention and Rehabilitation.

The commonly reported side effects that may result from exercise testing and training sessions may include palpitation, chest pain, shortness of breath, headache, nausea and/or fatigue.

Participants may find the questionnaires regarding HRQoL (Short Form 36) and anxiety and depression (HADS) distressing.

Mild discomfort is sometimes associated with blood draws, however, the procedure is quick, completed by a trained professional in a sterile environment and is associated with minimal discomfort.

6.3 Monitoring and reporting of adverse events/serious adverse events

The following definitions have been approved as part of Good Clinical Practice in Research:

Unanticipated problem

An unanticipated problem is defined as any incident, experience, or outcome that meets all of the following criteria:

Unexpected (in terms of nature, severity, or frequency) given (a) the research procedures that are described in the protocol-related documents, such as the REB-approved research protocol and informed consent document, or the Investigator Brochure (IB) or product monograph (PM); and (b) the characteristics of the research participant population being studied; and

Related or possibly related to participation in the research (possibly related means there is a reasonable possibility that the incident, experience, or outcome may have been caused by the [investigational product(s)] or procedures involved in the research); and

Suggests that the research places research participants or others at a greater risk of harm (including physical, psychological, economic, or social harm) than was previously known or recognized.

Adverse event

An adverse event is defined as any untoward medical occurrence in a research participant administered an investigational product and which does not necessarily have a causal relationship with this product. An AE can therefore be any unfavorable and unintended sign (including an abnormal laboratory finding, for example), symptom, or disease temporally associated with the use of an investigational product, whether or not related to the investigational product.

Serious adverse event

To ensure no confusion or misunderstanding of the difference between the terms "serious" and "severe," which are not synonymous, the following note of clarification is provided:

The term "severe" is often used to describe the intensity (severity) of a specific event (as in mild, moderate, or severe myocardial infarction); the event itself, however, may be of relatively minor medical significance (such as severe headache).

This is not the same as "serious," which is based on patient/event outcome or action criteria usually associated with events that pose a threat to a patient's life or functioning.

Seriousness (not severity) serves as a guide for defining regulatory reporting obligations.

After reviewing the various regulatory and other definitions in use or under discussion elsewhere, the following definition is believed to encompass the spirit and meaning of them all:

A serious adverse event (experience) or reaction is any untoward medical occurrence that at any dose:

- results in death;
- is life-threatening;
- requires inpatient hospitalization or prolongation of existing hospitalization;
- results in persistent or significant disability/incapacity; or
- is a congenital anomaly/birth defect.

The term "life-threatening" in the definition of "serious" refers to an event in which the patient was at risk of death at the time of the event; it does not refer to an event which hypothetically might have caused death if it were more severe.

Medical and scientific judgment should be exercised in deciding whether expedited reporting is appropriate in other situations, such as important medical events that may not be immediately life-threatening or result in death or hospitalization but may jeopardize the patient or may require intervention to prevent one of the other outcomes listed in the definition above. These should also usually be considered serious.

Examples of such events are intensive treatment in an emergency room or at home for allergic bronchospasm; blood dyscrasias or convulsions that do not result in hospitalization; or development of drug dependency or drug abuse.

All unanticipated problems/adverse events/serious adverse events will be recorded on the case report form (CRF) and in the source documents at the site of testing. A log for all unanticipated problems/adverse events/serious adverse events occurring in the study will be kept. The details of any unanticipated problems/adverse events/serious adverse events at each study visit, using the protocol-defined terminology, will be recorded.

The principal investigator and or study staff will educate the participants about unanticipated problems/adverse events/serious adverse events as well as the importance of reporting them to the study coordinator at study visits.

Anyone within the research team who becomes aware of unanticipated problems/adverse events/serious adverse events will report this to the principal investigator. The principal investigator will assess the unanticipated problems/adverse events/serious adverse event and provide the research participant with appropriate medical care as applicable. The principal investigator will report to the REB within 7 days only the local adverse events/serious adverse events that are deemed to be unanticipated problems.

The monitoring of these unanticipated problems/adverse events/serious adverse will be made in accordance with SOP C3-007.1 Safety Reporting Requirements.

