5.4.3 Intervention assessments

Participants in the Intervention Group will be asked to return their weekly wear time journals each week by dropping off into a study mail box on the Track in the Minto Prevention and Rehabilitation

Centre at the UOHI. They will also exchange their VTAP for a newly charged device and be provided with a new wear time log.

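### Section 6.3 ties non-serious adverse events to use of an undefined investigational product, leaving those in Controls and before VTAP issue open to under-recording

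*Combined protocol and SAP*

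**What the plan says.** Section 6.3 sets up three categories with different scope.

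- **Adverse event:** "any untoward medical occurrence in a research participant administered an investigational product". The definition goes on to require a sign, symptom or disease "temporally associated with the use of an investigational product, whether or not related to the investigational product". The product is not identified anywhere in the protocol.
- **Serious adverse event:** "any untoward medical occurrence that at any dose" meets a seriousness criterion. There is no limit to one arm or to users of a product.
- **Unanticipated problem:** possible causes include the product "or procedures involved in the research", but the event must also be unexpected and point to a greater risk than was known.

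On collection, staff are to teach participants about these events and the "importance of reporting them to the study coordinator at study visits". Details are recorded at each study visit in the terms that the protocol defines. A study-wide log is kept, and any research team member who learns of an event tells the principal investigator.

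On exposure and contact, everyone wears an activPAL3 for seven days before the first class and again in week 8. Only the Intervention arm receives the VTAP, after the first treadmill test and randomisation, for weeks 1 to 7 (Sections 5.1 and 5.4.2). Between the two assessments, "Participants in the Control Group will continue with their regular CR class schedule" (Section 5.1). Intervention participants exchange devices weekly and return journals by "dropping off into a study mail box on the Track" (Section 5.4.3, Intervention assessments). In Table 1 the only entries for weeks 2 to 7 are for the Intervention arm, and there is no adverse event row. Section 5.4, however, lists the eight weeks of on-site rehabilitation among the study-related visits of each participant.

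**The concern.** The adverse event definition reads as text for a trial in which everyone is given a product. Here the comparator is usual care, and one research procedure with a stated risk, the treadmill test, is first done before any VTAP is issued. Taken literally, the definition makes whether a minor event counts depend on the arm and on the week.

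The trial is meant to show whether the VTAP is usable and to inform a larger one. The protocol itself foresees skin irritation from the monitors (Section 6.2) and excludes patients with a history of postural hypotension (Section 5.3.1), so minor events matter to its purpose. If such events are in scope throughout weeks 1 to 7 in one arm and doubtful in the other, an apparent excess with the VTAP could come from the recording rule. Unequal study contact in Table 1 could add to this.

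**Working it through.** **1. Inputs.** 32 participants, 16 per arm (Section 5.6.1, taken as given because it serves only as a denominator). Two treadmill tests each, at weeks 1 and 8 (Table 1). The first test precedes randomisation and the VTAP (Section 5.1). VTAP in weeks 1 to 7 (Section 5.4.2). activPAL3 in the baseline week and week 8. Participation lasts nine weeks (Section 5.4). Cardiac risk is 6 per 10,000 tests = 0.06% (Section 6.2).

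**2. Treadmill tests outside the definition.** Planned tests: 32 × 2 = 64.

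| Reading of the product | Tests inside | Tests outside |
|---|---|---|
| VTAP only | 16 (Intervention, week 8) | 32 baseline + 16 Control week 8 = 48; 48/64 = 75% |
| VTAP and activPAL3 | up to 64 | 0 need fall outside |

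The first row is lenient: it counts the Intervention week-8 tests as inside although VTAP wear ends with week 7. If 15% of participants (the plan's 10% + 5%) missed week 8, each arm would have 16 × 0.85 = 13.6 tests then, and the share outside would be (32 + 13.6)/(32 + 27.2) = 45.6/59.2 = 77%.

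**3. Time outside the definition, wider reading.** Even if the activPAL3 counts, Controls wear no device in 9 − 1 (baseline) − 1 (week 8) = 7 weeks. That is 16 × 7 = 112 Control person-weeks with no product use for an event to be associated with. The Intervention arm wears the VTAP in those same weeks.

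**4. Scheduled contacts after the randomisation visit.** By Table 1, the Intervention arm has 7 (weeks 2 to 8) and Controls have 1 (week 8). At 16 per arm this is 112 against 16 person-visits. By Section 5.4, the rehabilitation weeks are study-related visits in both arms and the schedule is equal. The two passages do not agree.

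**5. Can the other categories catch what is left out?** Section 6.2 names palpitation, nausea and fatigue, among other symptoms, as common effects of exercise testing and training. When not serious, they are not serious adverse events. Because they are expected, they are not unanticipated problems. The adverse event category is the only place for them, and it is the restricted one. The log does not rescue them, since it is a log of events in these same categories.

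**6. Cardiac events at the tests.** Expected number: 64 × 0.0006 = 0.038 in all tests and 48 × 0.0006 = 0.029 in the 48. Chance of at least one: 1 − 0.9994^64 = 3.8% and 1 − 0.9994^48 = 2.8%. What is at stake is minor symptoms.

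**The case against.** Four arguments on the other side carry weight.

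- **Serious events are covered.** A reader might infer that harms in general, or cardiac events on the treadmill, go uncounted. The documents do not support that. The serious adverse event definition has no arm or product limit, and the unanticipated problem definition reaches research procedures. This stands, and it confines the point to non-serious events.
- **The product may include the activPAL3.** The primary objective evaluates both devices, and everyone wears an activPAL3 before the first test. The 75% is therefore conditional on one reading. This stands for the tests, but does not close the seven-week gap in Controls.
- **Visit frequency.** A reader might infer weekly adverse event collection in one arm and a single enquiry in the other. The protocol describes no adverse event question at the weekly device exchange, and Section 5.4 gives Controls study-related visits throughout. Every treadmill test is itself a study visit in both arms, so visit frequency has no bearing on the tests. What stands is the conflict between Section 5.4 and Table 1, and the absence of any scheduled enquiry.
- **No comparison is planned, and other documents may help.** Neither the feasibility measures in Section 5.5 nor the analyses in Section 5.6.2 compare adverse events by arm. The case report form and the safety reporting procedure cited in Section 6.3 are not available and may add detail. This lowers the urgency, but the definition in the protocol would still need correcting.

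**Conclusion.** The point holds for non-serious adverse events. Under either reading of the product, the stated rule puts Intervention events in weeks 1 to 7 inside the definition and Control events in those weeks outside it. If the product is the VTAP alone, it also leaves out all baseline treadmill tests and the Control week-8 tests, 48 of 64. With no enquiry scheduled and two accounts of what a study visit is, these events are open to under-recording, and any arm contrast in minor events would be hard to interpret.

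Under-counting itself is not established. Staff may record more than the definition requires, and the documents give neither a minor-event rate nor a capture probability from which to compute a bias. The conclusion assumes that the definition is applied as written and that Controls wear no study device between the baseline week and week 8. It is worth correcting before the results are used to design a larger trial, and it does not affect the sample size.

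**What to change.** - In Section 6.3, define an adverse event as any untoward medical occurrence in any consented participant, in either arm, from consent to the end of the week-8 monitor wear, including both treadmill tests. With this, 64 of 64 planned tests and all Control weeks are in scope.
- Reconcile Section 5.4 with Table 1 on what counts as a study visit.
- Add an adverse event row to Table 1 with one identical self-completed checklist for both arms at week 8. It should be returned with the feedback survey and not to the assessor, whom Section 5.4.3 (Follow-up assessments) requires to be blinded, because answers about skin reactions could reveal the arm.
- Base any arm comparison of non-serious events on that checklist only. Events learned of at other times are still logged and reported as Section 6.3 requires.

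A weekly form for Controls is not advised. It would add contact and cues about standing to the usual-care arm of a trial of sedentary behaviour.

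The cost is one short form and edits to Section 6.3, Section 5.4 and Table 1, with no extra visits or staff. The downsides are some recall loss in both arms and higher counts of minor events.
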